9.2 Demographic Variable Definitions

9.2.1 Age

Subject age will be calculated as the integer part of the number of years from date of birth to the date of signing the informed consent form, using the following formula:

Age = integer part of [(date of informed consent – date of birth + 1)/365.25].

9.2.2 Body Mass Index (BMI)

Body mass index (BMI) calculation: $BMI \text{ (kg/m}^2\text{)} = [\text{weight (kg)}] / [\text{height (m)}]^2$

9.3 Efficacy Endpoint Variable Definitions

9.3.1 Daily Nasal Symptoms Diary Assessments

Electronic diaries will be used by subjects during the single-blind placebo run-in period and during the first 12-weeks of the 24-week double-blind treatment phase in this study to capture daily nasal symptoms (i.e., symptom scores for nasal congestion, nasal discharge [anterior and/or posterior], facial pain or pressure sensation, and sense of smell) and the use of approved rescue medication after the Week 4 visit through Week 12 of the double-blind period. Subjects will be instructed to complete the electronic diary twice daily immediately before dosing (AM and PM).

Each morning and evening subjects will record their nasal symptom severity scores using the nasal symptoms scoring scale (Table 9.3) to evaluate their symptoms both immediately preceding the time of scoring (instantaneous), and based on reflection of symptoms over the past 12 hours, with regard to nasal congestion, nasal discharge (anterior and/or posterior), facial pain or pressure sensation, and sense of smell.

AM and PM assessment scores, and instantaneous and reflective scores, are all considered to be separate and distinct measures of nasal symptoms and will be analyzed separately.

Composite Score of Nasal Symptoms (CSNS): The CSNS is defined as the sum of the nasal congestion, nasal discharge and facial pain/pressure for each type of assessment (instantaneous or reflective) at each time point (AM or PM), resulting in four CSNS per day.

Table 9.3: Nasal Symptoms Scoring Scale

Score	Description
0	None
1	Mild – symptoms clearly present, but minimal awareness, and easily tolerated
2	Moderate – definite awareness of symptoms that is bothersome but tolerable
3	Severe – symptoms that are hard to tolerate, cause interference with activities or daily living

Note: Sense of smell, scored as 0=normal, 1=slightly impaired, 2=moderately impaired, 3=absent.

For statistical analyses, the daily AM and PM, instantaneous and reflective, individual nasal symptoms scores, and the CSNS will be averaged weekly, defined as the average of the daily scores for the 7 study days prior to the nominal day associated with each 7-day week; for example, for Week 2, Day 14 is the nominal day and the 7-day average is calculated based on study days 7 to 13.

Table 9.1 displays the efficacy windows defined for the 7-day average Daily Nasal Symptoms diary and CSNS for each study week from baseline (Visit 2) through Week 12 (Visit 5).

The 7-day average diary score will be derived for each nasal symptom (range 0-3) and CSNS (range 0-9) by time point (AM or PM) and measure (instantaneous or reflective). Thus, there are sixteen 7-day average scores representing the individual nasal symptoms scores: 2 (AM, PM) * 2 (instantaneous, reflective) * 4 nasal symptoms (congestion, discharge, facial pressure, sense of smell), and there are four 7-day average CSNS scores: 2 (AM, PM) * 2 (instantaneous, reflective).

The 7-day average AM, instantaneous CSNS score is the primary efficacy variable in this study.

Missing Diary Data

On any given study day, for time (AM, PM), or measure (instantaneous, reflective), if any of the 3 nasal symptom scores is missing then the CSNS score will be missing for that study day, time, and measure. For both individual symptoms and the CSNS, the average 7-day value will be missing only if there are missing values for all 7 days. For the first week (Study Days 2-6, Table 9.1), the average 5-day value will be missing only if there are missing values for all 5 days.

Intercurrent Events (IE)

If an intercurrent event occurs, under the composite strategy per the primary estimand, a worst score of '3' will be assigned to each of the daily nasal symptoms scores recorded on the day of the IE and for the remaining days in the week in which the IE occurs; that is, the 7-day average score will include actual scores for days up to the IE and then a worst score for diary days recorded on or after the day of the IE. Since CSNS is a composite score as defined above, a worst score of '9' is assigned. Subsequent 7-day average scores will be assigned a worst score for the remainder of the CSNS study period.

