### **9.1 Sample Size Determination**

Sample size assumptions were generated based on previous Phase 3 studies of OPN-375 in subjects with nasal polyposis and data from a study evaluating the change in maxillary and ethmoid opacification in CRS patients treated with an intramuscular dose of triamcinolone ([Pallanch 2013](#)). Based on the results for changes from baseline in morning symptoms among subjects with nasal polyps in the previous studies conducted with OPN-375, a sample of 111 subjects per group (333 total subjects) is sufficient to detect a 0.8 scale difference in morning symptoms score between treatments (OPN-375 vs placebo) using a 2-sided test at the 5% significance level with 88% power, and assuming a standard deviation (SD) of 1.9. This sample size is also adequate to detect an 11.3% difference between treatments in average percent opacification using a 2-sided test at the 5% significance level with 88% power, and assuming a SD of 27 percent. Approximately 333 subjects (111 subjects per group) will be randomized to have at least 120 subjects without nasal polyps be included. The sample size was estimated for the co-primary efficacy endpoints using Power Analysis and Sample Size Software (PASS 15) ([NCSS, 2017](#)).

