#### **9.3.1 Co-primary Endpoints**

- Change from baseline to the end of Week 4 in 7-day average instantaneous AM CSNS (evaluation of symptom severity immediately preceding the time of scoring):
  - nasal congestion
  - nasal discharge (anterior and/or posterior)
  - facial pain or pressure sensation

The baseline CSNS will be the average of the CSNS over the last 7 days of the placebo run-in period prior to randomization. The CSNS at Week 4 will be the average of the CSNS over the 7 days prior to nominal Study Day 28.

AND

- Change from baseline to Week 24/ET in the APOV in the ethmoid and maxillary sinuses (APOV is the average percentage of volume opacified across both maxillary and ethmoid sinuses (all 4 sinuses) at each time point)

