#### **9.3.3 Primary Estimand**

The primary efficacy estimand is the difference between each active treatment of twice-daily doses of 186 µg and 372 µg of OPN-375 and placebo for each of the co-primary endpoints.

For the primary estimand, intercurrent events will be addressed as follows:

1. Systemic corticosteroids use for CRS exacerbation or worsening of CRS nasal/sinus symptoms: a composite strategy will be employed with a poor score assigned to this event.
  - For CSNS, a value of '9' will be assigned. For APOV, a poor score is defined as follows: for a subject with a baseline APOV  $\geq 75\%$ , a value of '100%' is assigned; if baseline APOV  $< 75\%$ , a poor score is defined as baseline APOV + 25%. The rationale for assignment of a poor score is provided in the SAP. Also, further detail regarding the handling of a missing within-instrument data in these endpoints is provided in the SAP.
  - Systemic corticosteroid use for other indications will be considered a treatment and study discontinuation event (reference criteria 3).
2. Nasal surgery: composite strategy with poor scores assigned as above.
3. Treatment Discontinuation: treatment policy strategy; subjects may continue in the study until one of the following three mutually exclusive outcomes:
  - a. Subject completes Week 24/ET CT scan. In the absence of an intercurrent event (systemic corticosteroids, nasal surgery) use the endpoint value;
  - b. An intercurrent event (systemic corticosteroids for CRS exacerbation or worsening of CRS nasal/sinus symptoms, nasal surgery) occurs: Use composite strategy and assign poor score as described above (reference criteria 1,2);
  - c. Subject discontinues the study. Missing data due to study discontinuation following treatment discontinuation will be imputed; further detail on the imputation method is provided in the estimation section for each of the co-primary endpoints.

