2 INTRODUCTION

This Statistical Analysis Plan (SAP) has been developed after review of Sponsor Protocol OPN-FLU-CS-3205 (Amendment 6.0, dated 07 January 2022) and the corresponding electronic case report form (eCRF). This SAP describes the statistical methods to be used for the analysis and reporting of all efficacy and safety data collected during the conduct of Protocol OPN-FLU-CS-3205.

This SAP supersedes the statistical considerations identified in original Protocol OPN-FLU-CS-3205, as well as the SAP dated 19 April 2021, which is based on Protocol Amendment 4.1 and is the basis for the IASAP dated 8 June 2021. This SAP contains all changes incorporated into Protocol Amendment 6.0, and there are no deviations from this amendment presented in this SAP. If additional analyses are performed to supplement the planned analyses described in this SAP they will be identified as such in the Clinical Study Report (CSR).

This SAP is being written with consideration of the recommendations outlined in the following International Conference on Harmonization (ICH) Guidance for Industry documents:

- E9: Statistical Principles for Clinical Trials
- E9-R1 Addendum: Estimands and Sensitivity Analysis
- ICH E3: Structure and Content of Clinical Study Reports

This SAP also incorporates the recent FDA Guidance regarding the COVID-19 Public Health Emergency (PHE):

- FDA Guidance on the Conduct of Clinical Trials of Medical Products during COVID-19 Public Health Emergency: Guidance for Industry, Investigators, and Institutional Review Boards, (11 May 2020)

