7.1.3 Primary Estimand

The primary efficacy estimand is the difference between each active treatment of twice-daily doses of 186 μg and 372 μg of OPN-375 and placebo for each of the co-primary endpoints.

For the primary estimand, intercurrent events will be addressed as follows:

1. Systemic corticosteroids use for CRS exacerbation or worsening of CRS nasal/sinus symptoms: a composite strategy will be employed with a poor score assigned to this event.

For CSNS, a value of '9' will be assigned; further detail regarding the assignment of a worst score to the diary data are provided in Section 9.3.1. For APOV, a poor score is defined as follows: for a subject with a baseline APOV $\geq 75\%$, a value of '100%' is assigned; if baseline APOV $< 75\%$, a poor score is defined as baseline APOV + 25%.

The rationale for assignment of a poor score is provided in Section [7.1.4](#) below. Further detail regarding the handling of a missing POV in individual sinuses is provided in Section [9.3.2](#).

Systemic corticosteroid use for other indications will be considered a treatment and study discontinuation event (reference criteria 3c).

2. Nasal surgery: composite strategy with poor scores assigned as above.
3. Treatment Discontinuation: treatment policy strategy; subjects may continue in the study until one of the following three mutually exclusive outcomes:
 - a) Subject completes Week 24/ET CT scan. In the absence of an intercurrent event (systemic corticosteroids, nasal surgery) use the endpoint value;
 - b) An intercurrent event (systemic corticosteroids for CRS exacerbation or worsening of CRS nasal/sinus symptoms, nasal surgery) occurs: use composite strategy and assign poor score as described above (reference criteria 1, 2);
 - c) Subject discontinues the study. Missing data due to study discontinuation following treatment discontinuation will be imputed; further detail on the imputation method is provided in Section [7.1.5](#) for each of the co-primary endpoints.

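### SAP 9.3.1 does not carry the composite strategy cleanly into the Week 4 CSNS: an event on Days 22–27 is averaged with pre-event scores, and the 9s may depend on diary recording

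*SAP*

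**What the plan says.** Protocol 9.3.3 uses a composite strategy for systemic corticosteroids given for CRS: "For CSNS, a value of '9' will be assigned". Surgery is treated the same way: "Nasal surgery: composite strategy with poor scores assigned as above". SAP 7.1.3 repeats the rule and refers the reader onward: "For CSNS, a value of '9' will be assigned; further detail regarding the assignment of a worst score to the diary data" is placed in SAP 9.3.1. SAP 7.5.1, on the secondary diary endpoints, also applies 9 to the 7-day average CSNS, with the same pointer.

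SAP 9.3.1 then gives the derivation. In the event week, "the 7-day average score will include actual scores for days up to the IE and then a worst score for diary days", and the sentence limits those days to ones *recorded* from the event day on. For later weeks: "Subsequent 7-day average scores will be assigned a worst score for the remainder of the CSNS study period".

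Two other rules matter. SAP Table 9.1 sets the Week 4 window at Study Days 21 to 27. SAP 9.3.1 treats a 7-day average as missing only when all seven days are missing. SAP Section 2 states that "there are no deviations from this amendment presented in this SAP", and Section 11 does not list the event-week rule.

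**The concern.** Under a composite strategy the event is itself the outcome, so its value should not depend on how the subject felt beforehand. The blend makes the Week 4 value depend on the day of the event and on the scores before it. A subject who needed systemic corticosteroids or surgery near the end of the window can show a negative (improved) change on a co-primary endpoint.

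The word *recorded* adds a second dependence. If post-event diary days are blank and only recorded days receive the worst score, the missing-diary rule leaves an average made up of pre-event days. SAP 7.1.2 describes the surgery event as study discontinuation for nasal surgery, a setting in which recording may well stop.

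The pooled key secondary CSNS analysis inherits this handling (SAP 7.3 and 7.3.1). None of the planned alternative analyses tests a full 9:

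- The supplementary estimand uses treatment policy for corticosteroids and the same poor-score rules for its composite events.
- The observed-cases analysis ignores the events.
- The per-protocol exclusion examples include oral-steroid use and sinus surgery.

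**Working it through.** **Design figure.** The protocol states that 111 per group "is sufficient to detect a 0.8 scale difference in morning symptoms score between treatments" with 88% power, SD 1.9, two-sided 5%. The standard error is 1.9 × √(2/111) = 0.255; 0.8/0.255 = 3.14; 3.14 − 1.96 = 1.18, giving 88.0% (87.8% with the t distribution). The figure reproduces and is not in dispute. The 0.8 serves only as a yardstick.

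**Inputs.** The window (Days 21–27) and the worst score (9) come from the SAP. Baseline B and mean pre-event score a are assumptions, because neither document gives a baseline CSNS.

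**Blend, all days recorded.** An event on day d gives k = 28 − d days scored 9.

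Week 4 value = ((7 − k) × a + 9k) / 7; change = value − B. If 9 replaces the weekly average, change = 9 − B.

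With B = 6 and a = 4:

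| Event day | k | Week 4 value | Change | Change with full 9 |
|---|---|---|---|---|
| 21 | 7 | 9.00 | +3.00 | +3 |
| 22 | 6 | 8.29 | +2.29 | +3 |
| 23 | 5 | 7.57 | +1.57 | +3 |
| 24 | 4 | 6.86 | +0.86 | +3 |
| 25 | 3 | 6.14 | +0.14 | +3 |
| 26 | 2 | 5.43 | −0.57 | +3 |
| 27 | 1 | (6 × 4 + 9)/7 = 4.71 | −1.29 | +3 |

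**When the change is an improvement.** This requires a < (7B − 9k)/(7 − k):

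| Event day | B = 4.5 | B = 5 | B = 6 | B = 7 |
|---|---|---|---|---|
| 27 | 3.75 | 4.33 | 5.50 | 6.67 |
| 26 | 2.70 | 3.40 | 4.80 | 6.20 |
| 25 | 1.12 | 2.00 | 3.75 | 5.50 |
| 24 | none | none | 2.00 | 4.33 |
| 23 | none | none | none | 2.00 |
| 21–22 | none | none | none | none |

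**No post-event recording, literal reading.** For Days 22–27 the value is a, so any a < B is an improvement. For Day 21 all seven days would be missing, and so would the average.

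**Effect on an arm mean.** The gap to a full 9 is (7 − k)(9 − a)/7. With a = 4 and events spread evenly over Days 21–27, 7 − k averages 3, so the mean gap is 3 × 5/7 = 2.14 points per affected subject. If 1%, 2% or 5% of the arm are affected, the arm mean moves by 0.02, 0.04 or 0.11. Taking a from 3 to 5 widens the range to 0.017–0.129. In the extreme case that every affected subject has an event on Days 22–27 and records nothing afterwards, the gap is 9 − 4 = 5 points each, or 0.05 at 1% and 0.25 at 5%.

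**The case against.** **The protocol may mean 9 per day.** Protocol Section 9 leaves the definition of analysis variables to the SAP, and the protocol uses CSNS for both the daily and the averaged score: "The CSNS at Week 4 will be the average of the CSNS over the 7 days prior to nominal Study Day 28". On that reading SAP 9.3.1 implements the protocol. This stands in part. A reader might infer a plain contradiction and a false no-deviations statement, but the wording does not establish either. What remains is that the protocol does not say which it means, and that SAP 7.5.1 attaches the 9 to the 7-day average before pointing to a section that blends.

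**The lost-9 result depends on a literal reading.** SAP 9.3.1 also applies the worst score to the remaining days of the event week, which can be read to include unrecorded days. This stands as far as it goes: the text is ambiguous, and a pre-event-only average is a possible outcome rather than a certain one.

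**The illustration favours the concern.** With the same inputs, Days 21–25 all score as worsening. The exacerbation definition requires at least 3 days of worse symptoms, so pre-event scores would often already be raised. This stands, and is why the thresholds are shown.

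**A full 9 has its own cost.** It overwrites observed days and creates a cut-off: Day 27 scores 9, while Day 28 leaves Week 4 wholly observed. SAP 7.1.4 warns that a few extreme values can be influential. These are fair points, but the plan already accepts 9 for every later week.

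**Conclusion.** The point holds as a defect of derivation and wording in a co-primary endpoint. For events on Days 22–27, SAP 9.3.1 blends pre-event scores with 9s, and its reference to recorded days leaves open whether the 9s are applied at all when the diary stops. An event on Day 21 with the diary kept already gives a full 9, as does any event in an earlier week.

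The effect on a single subject can be large: 4.29 points for Day 27 at B = 6, a = 4. The effect on the trial is probably small, about 0.02 to 0.11 on an arm mean for 1% to 5% affected with diaries kept. The treatment contrast moves only as far as the arms differ. Event rates, baseline and prior scores are all assumed, and the documents do not show the direction of any bias.

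A reader might go further and say that treatment failures are counted as responders. The documents do not support that: the CSNS co-primary is a mean change analysed by MMRM, and there is no CSNS responder endpoint. The stated sample size and power are unaffected.

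**What to change.** In SAP 9.3.1, delete the reference to recorded days and assign 9 whether or not the diary was completed. Then choose one of the following:

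1. Assign 9 to the whole 7-day average for the event week and all later weeks.
2. Keep the daily blend, state in both documents that 9 is a daily value, list the rule in SAP Section 11, and add option 1 as a sensitivity analysis.

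The cost is a sentence or two, plus one additional analysis under option 2. Option 1 discards observed pre-event days in the event week. Under either option the same derivation must be used for Study OPN-FLU-CS-3206, because the key secondary CSNS analysis pools the two studies.

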9.3.2 Quantitative (Volumetric) Measurement of CT Scan Image

The protocol for quantitative (volumetric) measurement of CT scan imaging is based on the Image Review Charter (IRC) – Revision C, (29 January 2020). Quantitative measurement of Sinus Volume and Opacification Volume will be performed by a trained analyst under the supervision of a Biomedical Engineer using a validated software system as described in the IRC.

The following quantitative variables are defined for each of the four sinuses: Maxillary (Left, Right), Ethmoid (Left, Right).

Sinus Volume (SV): the total volume of the specified sinus cavity regardless of the amount of mucosal inflammation that may be present. Total Sinus Volume will consist of both the soft tissue and air signal within the specified sinus. Sinus Volume will be reported in cubic millimeters.

Opacification Volume (OV): the total volume of the soft tissue and mucosal inflammation as visualized in the specified sinus. Opacification Volume will be reported in cubic millimeters.

Percentage of Opacified Volume (POV): $POV = OV/SV \cdot 100\%$

Missing Volumetric Measurements

Volumetric measurements (SV, OV) of a sinus may be missing due to technical issues that are unrelated to disease measurement; these measurements are reported as 'Unable to Assess.'

If the volumetric measurements in any sinus are missing at baseline, then the subject will be excluded from the FAS population. If either of the volumetric measurements in any sinus is missing at Week 24/ET, then the volumetric measurement for that sinus will be replaced by the baseline volumetric measurement.

Average Percentage of Opacified Volume (APOV)

APOV is the average percentage of opacified volume across both maxillary (L, R) and ethmoid (L, R) sinuses (all 4 sinuses) at each time point (Baseline, Week 24/ET). Larger values of APOV,

i.e., higher percentages of opacified volume, indicate greater severity of CRS; therefore, negative values for change from baseline APOV indicate improvement from baseline.

APOV-E is the average percentage of opacified volume in the ethmoid (L, R) sinuses at each time point (Baseline, Week 24/ET).

APOV-M is the average percentage of opacified volume in the maxillary (L, R) sinuses at each time point (Baseline, Week 24/ET).

Worst Percentage of Opacified Volume (WPOV)

WPOV is the worst sinus across the maxillary (L, R) and ethmoid (L, R) sinuses (all 4 sinuses) at baseline. In the event of a tie, the rule is: use the right sinus, then use the ethmoid sinus.

WPOV-E is the worst ethmoid (L, R) sinus at baseline. In the event of a tie, the rule is: use the right sinus.

WPOV-M is the worst maxillary (L, R) sinus at baseline. In the event of a tie, the rule is: use the right sinus.

The endpoint analyzed is the change from baseline to Week 24/ET in the WPOV sinus; this is similarly defined for WPOV-E, WPOV-M.

9.3.3 SNOT-22 Total and Domain Scores

SNOT-22 is a subject-completed questionnaire that consists of 22 symptoms and social/emotional consequences of their nasal disorder. Each item is rated as follows: 0=no problem, 1=very mild problem, 2=mild or slight problem, 3=moderate problem, 4=severe problem, 5=problem as bad as it can be. The SNOT-22 is validated in CRS ([Hopkins 2009](#)). The recall period is the past 2 weeks.

Five domain scores will be derived from the SNOT-22 for efficacy evaluation (Table 9.4): Rhinologic Symptoms; Extra-Nasal Rhinologic symptoms, Ear and Facial Symptoms; Sleep Function; Psychological Issues; and the total score (sum of all items).

Table 9.4: SNOT-22 Domain and Total Scores

Domain	Sum of Items	Range
Rhinologic Symptoms	1, 2, 3, 6, 21, 22	0-30
Extra-Nasal Rhinologic Symptoms	4, 5, 6	0-15
Ear/Facial Symptoms	2, 7, 8, 9, 10	0-25
Psychological Dysfunction	14, 15, 16, 17, 18, 19, 20	0-35
Sleep Dysfunction	11, 12, 13, 14, 15	0-25
TOTAL SCORE	Sum of all 22 items	0-110

